4. LIST OF ABBREVIATIONS AND DEFINITIONS OF TERMS

The following abbreviations and specialist terms are used in this study protocol.

Table 4: Abbreviations and Specialist Terms

Abbreviation	Definition
AE	adverse event
██████████	██████████
BMI	body mass index
██████████	██████████
CAG	cytosine, adenine, and guanine
██████████	██████████
██████████	██████████
██████████	██████████
CAP	CAG-Age-Product
CFR	Code of Federal Regulations
██████████	██████████
██████████	██████████
████	██████████
CI	confidence interval
████	██████████
COVID-19	coronavirus disease 2019
CS	clinically significant
C-SSRS	Columbia–Suicide Severity Rating Scale
██████████	██████████
████	██████████
████	██████████
eCRF	electronic case report form
ECG	electrocardiogram
EC	Ethic Committee
ET	Early Termination
FDA	Food and Drug Administration
FSH	follicle-stimulating hormone

Abbreviation	Definition
GCP	Good Clinical Practice
GMP	Good Manufacturing Practice
HD	Huntington's Disease
HD-CAB	Huntington's Disease Cognitive Assessment Battery
HIV	human immunodeficiency virus
HP	healthy participant(s)
HTT	Huntington gene
ICF	informed consent form
ICH	International Council for Harmonization of Technical Requirements for Pharmaceuticals for Human Use
ID	a participant identification
IEC	independent ethics committee
IP	investigational product
IRB	institutional review board
IRT	interactive response technology
MedDRA	Medical Dictionary for Regulatory Activities
MoCA	Montreal Cognitive Assessment
mRNA	messenger ribonucleic acid
NCS	not clinically significant
NMDA	N-methyl-D-aspartate
NSF	National Sleep Foundation

Abbreviation	Definition
PAM	positive allosteric modulator
[REDACTED]	[REDACTED]
[REDACTED]	[REDACTED]
[REDACTED]	[REDACTED]
PK	pharmacokinetic
PO	by mouth
[REDACTED]	[REDACTED]
[REDACTED]	[REDACTED]
QTcF	QT corrected according to Fridericia's formula
SAE	serious adverse event
SAP	statistical analysis plan
SD	standard deviation
SOC	system organ class
SUSAR	suspected unexpected serious adverse reaction
Study partner	Synonymous with care partner
TEAE	treatment-emergent adverse event
TFC	Total Functional Capacity
THC	tetrahydrocannabinol
UHDRS	Unified Huntington's Disease Rating Scale
UP	unanticipated problem
USM	urgent safety measure
[REDACTED]	[REDACTED]

5. INTRODUCTION

Huntington's Disease (HD) is a rare hereditary neurodegenerative disease characterized by specific motor symptoms, including chorea and rigidity, and deterioration of psychiatric and cognitive function. The motor symptoms can manifest at any age, after which disease progression leads to incapacitation and death. Before the appearance of motor symptoms, psychiatric and cognitive dysfunction predominate (Tabrizi 2012). Cognitive impairment is always present in the course of the disease, even in premanifest gene carriers (Cardoso 2017).

The mechanisms of cognitive changes in HD have not been fully described, but changes in glutamatergic neurotransmission appear to be involved. Reduced glutamate in the posterior cingulate cortex has been correlated with cognitive dysfunction in early manifest HD (Unschuld 2012). N-methyl-D-aspartate (NMDA) receptors are a subtype of glutamate receptor with a fundamental and well documented role in regulating synaptic strength, health, and plasticity (Vyklicky 2014, Yao 2017). NMDA receptors have been found to be dysfunctional in the postmortem brains of patients with HD (Albin 1990). Together, these data suggest that lowered NMDA receptor tone may contribute to cognitive dysfunction in HD (Paul 2013).

Preclinical data illustrate that patients with HD have reduced plasma levels of a specific oxysterol, 24(S)-hydroxycholesterol (Leoni 2013). This molecule acts as an endogenous positive allosteric modulator (PAM) of the NMDA receptor (Paul 2013) and has been correlated with performance on several cognitive tasks in HD (Lewis 2019). SAGE-718 is a novel oxysterol-based PAM of NMDA receptors with the potential to restore NMDA receptor tone to ameliorate cognitive deficits in HD. SAGE-718 only affects receptor function in the presence of endogenous glutamate, thus it does not directly activate the receptor and is not expected to cause NMDA receptor-associated excitotoxicity.

The effect of SAGE-718 on cognitive and function outcomes in participants with HD will be evaluated in a randomized, placebo-controlled, double-blind, parallel group and normative comparison study. Additional data on the effects of SAGE-718 in participants with HD will be collected throughout, including assessments of neuropsychiatric and motor symptoms.

5.1. Dose Justification

SAGE-718 has been well tolerated in both healthy participants (HP) and a small cohort of participants with HD in previous clinical studies. However, based on nonclinical findings, the United States Food and Drug Administration (FDA) imposed a median maximum concentration (C_{max}) cap of 45 ng/mL. To date, clinical studies with SAGE-718 have used doses that resulted in exposures within this cap and no related adverse events (AEs) leading to discontinuation have been reported. For additional information on the exposure caps, see the SAGE-718 investigator's brochure.

From a previous study of SAGE-718 administered as an oral solution in healthy participants, repeat doses of 1 mg and a single dose of 3 mg demonstrated evidence consistent with NMDA target engagement. From a 14-day study of SAGE-718 administered as an oral solution in participants with HD, repeat doses of 1 mg showed beneficial effects on cognition assessments. Similarly, from a 14-day study of SAGE-718 administered as a solid tablet in participants with Parkinson's Disease, repeat doses of 3 mg when taken with a meal containing approximately 30 g of dietary fat showed beneficial effects on cognition assessments. The pharmacokinetic

(PK) exposures in the above scenarios were similar, with individual C_{max} values ranging from 19.7 to 29.7 ng/mL.

In the present study, SAGE-718 will be administered as a lipid based softgel formulation at a daily dose of 1.2 mg. The lipid formulation has improved bioavailability characteristics compared to solution and tablet forms. [REDACTED]

[REDACTED]

[REDACTED]

[REDACTED]

6. STUDY OBJECTIVES AND ENDPOINTS

6.1. Objectives and Endpoints

Objectives	Endpoints
Primary 
To assess the magnitude of the baseline difference between participants with Early Huntington's Disease (HD) and healthy participants (HP) with respect to measures of cognitive performance.	
Difference in baseline measures of the Huntington's Disease Cognitive Assessment Battery (HD-CAB) cognitive composite score in participants with HD and HP.
Secondary 
To evaluate safety and tolerability of SAGE-718 in participants with HD.	
Safety and tolerability of SAGE-718 as assessed by the incidence of adverse events (AEs)/serious adverse events (SAEs), and by changes in vital signs and clinical laboratory parameters.

- To evaluate additional safety and tolerability parameters of SAGE-718 in participants with HD.
- Change from Baseline and between-group effects (SAGE-718 and placebo) for [REDACTED], electrocardiograms (ECGs), and responses on the Columbia-Suicide Severity Rating Scale (C-SSRS).

7. INVESTIGATIONAL PLAN

7.1. Overall Study Design

This is a randomized, placebo-controlled, double-blind, parallel group study with a 28-day treatment duration to evaluate the effects of SAGE-718 on functioning capacity, safety, and tolerability in participants with early manifest HD. Participants will be adults with genetically-confirmed expansion of the Huntington (HTT) gene cytosine, adenine, and guanine (CAG) trinucleotide repeat at screening who meet diagnostic criteria detailed in the inclusion criteria below [including Unified Huntington's Disease Rating Scale (UHDRS) scores and CAG-Age-Product [CAP] scores within specific ranges].

HP enrolled in the study will follow the same assessment schedule as participants with HD, but will not receive SAGE-718 or placebo, and will complete assessments only on performance-based tests (HD-CAB [REDACTED]), not HD-specific measures of functioning and HD symptomatology.

An adult study partner for participants with HD is optional but highly recommended for each participant with HD to support completion of study activities and to answer questions about the participant's condition. For prospective participants with HD and study partners (if applicable), the study will begin with the informed consent process.

Screening, safety, and efficacy assessments will be performed according to the schedule presented in [Table 1](#) (HD) and [Table 2](#) (HP). [REDACTED]

Screening assessments will be performed to determine eligibility. Participants and study partners (if applicable) will receive training on the study procedures and devices.

Eligible participants with HD will be randomized 1:1 in a stratified manner based on previous intake of antisense oligonucleotide drugs (yes/no) to receive 1.2 mg of SAGE-718 or placebo for up to 28 days. Beginning on Day 1 and continuing through Day 28, participants with HD will self-administer blinded investigational product (IP) once per day in the morning. At clinic visits, participants with HD will take the IP under staff supervision, [REDACTED]

[REDACTED] Study staff will dispense sufficient IP for daily administration until the next scheduled study visit. Adherence to the dosing regimen will be assessed at each in-clinic visit by examination of the used packaging and counting any returned tablets.

During the Treatment Period, participants with HD will be able to receive IP as long as there are no dose-limiting safety/tolerability concerns. Participants with HD who discontinue IP early should complete the remaining study visits as scheduled, unless the participant with HD withdraws consent or loses the capacity to grant consent. If a participant with HD withdraws from the study or stops study participation, an early termination (ET) visit should be conducted.

After completing the Treatment Period or Reliability Assessment Period, all participants will return to the clinic for follow-up visits on Day 42 (± 2 days) to collect continued safety and efficacy data.

7.1.1. Screening Period

The Screening Period begins with the informed consent process for prospective participants, including study partners for participants with HD. Subsequent screening assessments will be performed between Day -28 and Day -1 for participants with HD and HP to determine eligibility, including assessments of cognitive function.

7.1.2. Baseline Period

The Baseline Period will be completed by Day 1 for participants with HD and HP. During this period, participants will visit the clinic for confirmation of continued eligibility and collection of baseline cognitive and safety data.

7.1.3. Treatment Period

Eligible participants with HD will be randomized 1:1 to receive SAGE-718, or placebo for 28 days. Beginning on Day 1 and continuing through the 4-week treatment period, participants with HD will self-administer blinded 1.2 mg SAGE-718 (as 1.2-mg softgel lipid capsules) or placebo, once per day in the morning. Participants who utilize the ± 2 day window at Day 28 should continue to self-administer IP within the visit window. HP will not receive SAGE-718 or placebo.

At clinic visits, participants with HD will take the IP under staff supervision, [REDACTED]

[figure not shown]
[REDACTED] Study staff will dispense sufficient IP for daily administration until the next scheduled study visit. Adherence to the dosing regimen will be assessed at each in-clinic visit by examination of the used packaging and counting any returned tablets.

During the Treatment Period, participants with HD will be able to receive IP as long as there are no dose limiting safety/tolerability concerns. Participants with HD who discontinue IP early should complete the remaining study visits as scheduled, unless the participant with HD withdraws consent or loses the capacity to grant consent. If a participant with HD withdraws from the study or stops study participation early, an ET visit should be conducted.

7.1.4. Follow-up Period

After completing the Treatment Period or Reliability Assessment Period, all participants will return to the clinic for follow-up visits on Day 42 (± 2 days) to collect continued safety and efficacy data (Table 1 and Table 2).

Figure 1: Study Design

Abbreviations: [REDACTED] HD = Huntington's Disease,
HD-CAB = Huntington's Disease Cognitive Assessment Battery. HP = healthy participants, PO = by mouth, [REDACTED]

^A Participants with HD:

b [REDACTED]

c [REDACTED]

d HP: (Assessments Only)

e [REDACTED]

f [REDACTED]

[REDACTED]

7.2. Number of Participants

Approximately 40 participants with early HD ($n = 20$ per treatment arm) will be randomized in the study to obtain 32 evaluable participants with HD ($n = 16$ per treatment arm). Additional participants may be randomized if the early discontinuation rate is higher than expected (20%). Approximately 40 matched healthy participants (eg. age, sex, race and education) will be enrolled in an “assessment only” arm and will complete specific assessment procedures following the same schedule as the treatment arm participants.

7.3. Treatment Assignment

Eligible participants with HD will be randomized 1:1 to receive 1.2 mg of SAGE-718, or placebo for up to 28 days. Additional details on randomization and blinding are provided in Section 9.5.

7.4. Dose Criteria

During the Treatment Period, participants with HD will be able to receive IP as long as there are no dose limiting safety/tolerability concerns.

7.4.1. Stopping Criteria

If clinical events suspicious for seizure occur after Screening, IP should be discontinued immediately with appropriate clinical follow-up, including electroencephalography (EEG), repeat serum chemistry, urinalysis, and drug/alcohol tests.

7.5. Criteria for Study Termination

Sage Therapeutics may terminate this study or any portion of the study at any time for safety reasons including the occurrence of AEs or other findings suggesting unacceptable risk to participants, or for administrative reasons. In the event of study termination, Sage Therapeutics will provide written notification to the investigator. Investigational sites must promptly notify their institutional review board (IRB)/independent ethics committee (IEC), where required, and initiate withdrawal procedures for participating participants.

7.6. End of Study Definition

The end of the study is defined as the date of the last visit of the last participant in the study. A participant is considered to have completed the study if he/she has completed all phases of the study including the last visit.

8. SELECTION AND WITHDRAWAL OF PARTICIPANTS

8.1. Participant Inclusion Criteria

Each eligible participant must:

For All

1. Be capable of providing informed consent, in the opinion of the investigator.
2. Have signed an informed consent form (ICF) prior to any study-specific procedures being performed.
3. Agree to adhere to the study requirements.
4. Be capable of complying with study procedures, in the opinion of the investigator. The investigator may determine a participant's capability of being able to complete the Driving Simulator at Screening based on the outcome of the simulator sickness screening interview.
5. Be at least 25 years old but no older than 65 years of age at Screening.
6. Currently hold a valid driver's license, 5+ years driving experience, and participants opting in the driving simulator assessment are currently driving at least 1 × weekly.
7. Agree to refrain from drugs of abuse for the duration of the study and from alcohol during the 48 hours preceding each study visit.

Additional criteria for participants with HD only

8. Be ambulatory (use of assistance devices such as a walker or cane is acceptable, as is occasional use of wheelchair. Individuals requiring a wheelchair on a regular basis are excluded), able to travel to the study center, and, judged by the investigator, is likely to be able to continue to travel to the study center to complete study visits for the duration of the study.
9. Have:
 - a. Genetically confirmed disease with CAG expansion ≥ 36 .
 - b. At Screening, UHDRS TFC > 6 and < 13 , suggesting no more than a moderate level of functional impairment.
 - c. No features of juvenile HD.
10. CAP score > 70 , as calculated using the CAP formula: $AGE \times (CAG - 30) / 6.49$.
11. Score of 15 to 25 (inclusive) on the MoCA at Screening, indicating the presence of cognitive impairment.
12. Be willing to invite a study partner, if available, who is reliable, competent, and at least 18 years of age to participate in the study.
13. Agree, if female, to use at least one method of highly effective contraception (refer to Section 9.2.4 for further details on acceptable forms of contraception) during participation in the study and for 155 days following the last dose of IP, unless they are postmenopausal (defined as no menses for 12 months without an alternative medical

cause and confirmed by follicle-stimulating hormone [FSH] > 40 mIU/mL), surgically sterile (hysterectomy, bilateral salpingectomy, or bilateral oophorectomy), or does not engage in sexual relations which carry a risk of pregnancy.

14. Agree, if male, to use an acceptable method of effective contraception for the duration of study and for 215 days after receiving the last dose of the IP, unless the participant does not engage in sexual relations which carry a risk of pregnancy. Acceptable methods of effective contraception are listed in Section 9.2.4.
15. Agree, if male, to abstain from sperm donation during the Treatment Period and for 215 days after receiving the last dose of IP.

Additional criteria for HP only

16. Score ≥ 26 on the MoCA at Screening.
17. Have no known family history of HD; or, have known family history of HD but have genetic test results available that show a normal CAG repeat length for both HTT alleles (<36).

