Continuous data will be summarized in terms of the number of participants, mean, standard deviation (SD), minimum value, first quartile (Q1), median, third quartile (Q3), and maximum value. Categorical data will be summarized using frequency counts and percentages.

Analysis Sets

The All Randomized Set will include all participants who have been randomized and will be used to describe participant disposition.

The Safety Set will include all participants with HD who were administered IP or HP and will be used to describe the safety data. The Safety Set will be further subdivided to describe participants with HD and healthy participants separately.

The Full Analysis Set will include all participants who meet the eligibility criteria and have at least 1 baseline assessment of HD-CAB (participants with HD and HP).

The Full Analysis Set 1 will include all participants who initiate IP and have baseline and at least 1 postbaseline efficacy evaluation (participants with HD only).

The Full Analysis Set 2 will include all participants with HD who initiate IP or HP who meet eligibility criteria and have baseline and at least 1 postbaseline efficacy evaluation (participants with HD and HP).

The Healthy Participant Set will include all the healthy participants who meet the eligibility criteria and have more than one evaluation (baseline and at least one postbaseline).

Efficacy Analysis

Baseline differences between participants with HD and HP will be assessed across candidate endpoint using T-test. The mean differences, its 95% confidence interval (CI) and corresponding p value will be reported. For a given endpoint, if the 95% CI does not span zero, then it will be concluded that the participants with HD are statistically significantly different from their healthy comparators at Baseline

for that endpoint; otherwise, it will be concluded that there is not enough evidence to declare them statistically different.

[REDACTED]

[REDACTED]

[REDACTED]

[REDACTED]

[REDACTED]

[REDACTED]

[REDACTED]

Safety Analysis

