13.5. Efficacy Analysis

Efficacy data will be summarized using appropriate descriptive statistics and other data presentation methods, where applicable; participant listings will be provided for all efficacy data. Participants will be analyzed according to randomized treatment.

Baseline differences between participants with HD and HP will be assessed across candidate endpoint based on enrollment set using T-test. The mean differences, its 95% confidence interval (CI) and corresponding p value will be reported. For a given endpoint, if the 95% CI does not span zero, then it will be concluded that the participants with HD are statistically significantly different from their healthy comparators at Baseline for that endpoint; otherwise, it will be concluded that there is not enough evidence to declare them statistically different.

Additional analyses will be detailed in the SAP.

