3. STUDY OBJECTIVES

3.1. Primary Objective

- To assess the magnitude of the baseline difference between participants with early Huntington's Disease (HD) and healthy participants (HP) with respect to measures of cognitive performance.

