8.3. Efficacy Analysis

8.3.1. Definition of Efficacy Variables

8.3.1.1. Primary Efficacy Assessment and Estimand

The main interest of the primary analysis in this trial is to estimate the baseline differences between participants with HD and HP in HD-CAB composite outcome. This is a comparison between two populations without establishing a treatment effect and without potential intercurrent events. Therefore, we will not present an explicit definition of an estimand in this analysis.

The HD-CAB is a cognitive assessment battery developed for HD patients by [Stout et al. \(2014\)](#). The HD-CAB will be assessed on Screening Period (Day -28 to -2), pre-dose on Day 1, post-dose on Day 14 and Day 28, and during follow-up on Day 42.

HD-CAB consists of 6 subtests and each variable will be used to calculate HD-CAB composite score as outlined in [Table 2](#). If at least 1 out of 6 HD-CAB subtests are missing, the HD-CAB composite score will be set to missing.

Table 2. HD-CAB Test Variables

Subtest Name (Assessment Type)	Cognitive Function Assessed	Variables	Score Range		Interpretation of Raw value	Recode
			Min.	Max.		
Symbol Digit Modalities Test (Paper)	Visuospatial attention, processing speed, working memory	Number of correctly coded items	0	110	High score indicates better performance	Not Needed; Use raw score
One Touch Stockings of Cambridge (Computer)	Planning, working memory	Mean time to reach a correct response (sec), averaged across all 10 trials	Not defined	Not defined	High score indicates worse performance	Part 1: Divide scores by 1000 to convert scores from milliseconds to seconds Part 2: Multiply scores by -1 so that higher values represent

Subtest Name (Assessment Type)	Cognitive Function Assessed	Variables	Score Range		Interpretation of Raw value	Recode
			Min.	Max.		
						better performance
Trail Making Test: Trail B (Paper)	Flexibility, visuospatial attention, psychomotor speed	Time (seconds) to complete the task	0 sec	240 sec	Higher value indicates worse performance	Multiply raw values by -1 so that higher values represent better performance
Hopkins Verbal Learning Test-Revised (Paper)	Verbal memory	Total correct recall trials over the 3 learning and 1 delayed recall trials	0	48	High score indicates better performance	Not Needed; Use raw score

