8.3.3.1. Primary Analysis

The primary efficacy endpoint is the difference between participants with HD and HP in baseline measures of the HD-CAB composite z-score standardized using mean and standard deviation from healthy participants. This primary endpoint will be analyzed using T-test. The mean difference, its standard error (SE) and 95% confidence interval (CI) and corresponding p-value will be reported.

A scatterplot showing the composite scores in two cohorts with mean \pm standard error of the mean (SEM) bars and a boxplot comparing the distribution in two groups will be provided.

[figure not shown]

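### Do the non-overlapping MoCA entry ranges for HD and healthy participants mean the primary objective or the conclusion rule must be reworded?

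*Protocol*

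**What the plan says.** Protocol 8.1, criterion 11, requires of participants with HD a "Score of 15 to 25 (inclusive) on the MoCA at Screening, indicating the presence of cognitive impairment". Criterion 16 requires of HP a "Score ≥ 26 on the MoCA at Screening". The two ranges share no value. Protocol 11.1.1 describes the MoCA as a global screen that includes executive function and memory, with 26 or more as normal. Protocol 11.2 lists executive function and learning and memory among the domains of the efficacy battery.

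The primary objective opens "To assess the magnitude of the baseline difference between participants with Early" in Protocol 6.1, and SAP 3.1 repeats it. SAP 8.3.1.1 sets no estimand, on the ground that "This is a comparison between two populations without establishing a treatment effect and without potential intercurrent events". SAP 8.3.3.1 compares the groups by t-test on "baseline measures of the HD-CAB composite z-score standardized using mean and standard deviation from healthy participants". Under Protocol 13.5, when the 95% interval excludes zero, "it will be concluded that the participants with HD are statistically significantly different from their healthy comparators at Baseline for that endpoint"; the synopsis has the same rule.

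Protocol 7.2 gives age, sex, race and education as examples of matching factors. MoCA is not among them.

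**The concern.** The objective asks for a magnitude, and selecting on a correlate of the outcome can move a magnitude. The HP floor removes healthy adults with weaker cognition. The HD window removes people with HD who score 26 or more, or below 15. Matching on demographics does not undo either step, and the primary t-test has no covariates. The three sensitivity analyses in SAP 8.3.3.2 deal only with the time limit on Trail Making B.

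Neither the objective nor the conclusion rule mentions the MoCA ranges. A reader who saw only those two passages could take the estimate as the difference between early HD and healthy adults in general, and could carry it into the planning of a later trial with different entry criteria.

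**Working it through.** **The plan's own figure.** Protocol 13.8 plans 40 per group, d = 0.63 and two-sided alpha 0.05. By normal approximation, 0.63 × √(40/2) = 2.817; 2.817 − 1.960 = 0.857; Φ(0.857) = 0.804. The noncentral t gives 0.795. The stated 80% power reproduces and is not in question. The expected 95% half-width is t(0.975, 78) × √(2/40) = 1.991 × 0.2236 = 0.445 SD.

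**Size of the selection part.** The documents do not give the inputs, so all of the following are assumptions: MoCA and composite bivariate normal with correlation r = 0.3 to 0.5; a share p = 20 to 30% of matched adults below 26; HD MoCA SD 4 with mean m varied; equal composite SDs.

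- HP floor: the HP mean rises by r × φ(c)/(1 − p), with c = Φ⁻¹(p). For p = 0.2, φ(c)/(1 − p) = 0.280/0.8 = 0.350. For p = 0.3, it is 0.348/0.7 = 0.497. The rise runs from 0.3 × 0.350 = 0.105 to 0.5 × 0.497 = 0.248 SD.
- HD window, with continuity correction: E = [φ(a) − φ(b)]/[Φ(b) − Φ(a)], where a = (14.5 − m)/4 and b = (25.5 − m)/4. The HD mean shifts by r × E.
- Widening of the gap = r × [φ(c)/(1 − p) − E].

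| HD MoCA mean m | E | Widening (SD) |
|---|---|---|
| 23 | −0.399 | 0.225 to 0.448 |
| 22 | −0.261 | 0.183 to 0.379 |
| 21 | −0.129 | 0.144 to 0.313 |
| 20 | 0 | 0.105 to 0.248 |
| 19 | 0.129 | 0.066 to 0.184 |
| 18 | 0.261 | 0.027 to 0.118 |
| 17 | 0.399 | −0.025 to 0.049 |
| 16 | 0.546 | −0.098 to −0.015 |

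Two rows as examples. At m = 23 the top is 0.5 × (0.497 + 0.399) = 0.448. At m = 16 the bottom is 0.5 × (0.350 − 0.546) = −0.098. The result depends on m, which the documents do not give. SAP 8.3.1.1 calls this HD cohort relatively more progressed than the published one, so the higher means cannot be favoured.

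**Effect of standardising to HP.** The HP mean cancels in HD minus HP. A narrower HP SD would enlarge the z-difference by 2 to 7% (SD ratio 0.981 to 0.935) if it acted equally on all six subtests. A common rescaling leaves the t-test unchanged.

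**Who the passages refer to.** SAP 8.3.3 runs the primary analysis on the Full Analysis Set. SAP 7.1 builds that set from randomised HD participants and HP who meet eligibility. Protocol 7.1 and SAP 5.1 describe the HD participants by reference to the inclusion criteria. The conclusion rule speaks of the participants with HD and their comparators, meaning the enrolled groups. In SAP 8.3.1.1 the phrase about two populations explains why no estimand is set; it makes no claim about patients outside the trial.

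**What rewording would alter.** Eligibility, enrolment, data, composite, t-test, interval, sample size and power would all stay the same. Covariate adjustment is no alternative: without overlap in MoCA, a model cannot separate disease from selection.

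**The case for a change.** The strongest case for a change is that the goal is a magnitude, that disclosure in the eligibility section does not by itself limit an objective written for early HD and healthy participants, and that one sentence costs little. It adds that low MoCA in HD is partly the disease, but that this does not account for the HP floor.

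Much of this stands. The ranges do not overlap, the domains are shared, and no readable text names the limit, although redactions in the efficacy sections prevent certainty. The estimate should not be carried over to early HD at large.

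It does not follow that the plan needs editing. Other criteria also narrow the reach of the estimate (functional capacity range, CAP score, driver's licence), and objectives do not normally restate them. Comparing cognitively impaired HD participants with cognitively normal controls fits a study whose title calls it a normative comparison and whose drug is aimed at cognitive deficits. A firm statement that the difference includes a selection effect would also claim too much, because the effect could be near zero or reversed. Applying it to every candidate endpoint would go further still, since domain overlap is shown only for the HD-CAB. A protocol amendment would need ethics re-approval (Protocol 16.1).

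A simulation gives larger figures, with d of about 0.5 from the cut-offs alone at r = 0.3. It assumes no disease effect on either measure. That is an extreme case for participants with genetically confirmed HD and reduced functional capacity, and it does not measure the problem here.

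**Conclusion.** The observation is correct, but it does not call for a change. Followed as written, the plan gives a valid test and interval for HD participants with MoCA 15 to 25 against HP with MoCA 26 or more, and its definitions already tie the comparison to those groups. What is missing is a sentence on generalisation that the published criteria imply and that a competent report author would supply in the discussion.

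The selection part lies between −0.10 and 0.45 SD for HD MoCA means of 16 to 23, given r of 0.3 to 0.5, 20 to 30% of matched adults below 26, and an HD MoCA SD of 4. None of these inputs comes from the documents, so the range is an illustration and should not be quoted as a share of the planning effect of 0.63.
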